Fifteen participants (10 completers estimating a very conservative attrition rate of 50%) will be recruited at the Tulsa Day Center (TDC), a private, non-for-profit organization in Tulsa, OK, continuously operating in the city for over 40 years. TDC offers shelter and daytime activities, including medical services, to about 250 homeless people every day. Participants will be pre-selected for participation by TDC staff based on their history of problematic behaviors (Table 1). All participants will be between 18 and 65 years of age, inclusive. TDC staff will collect information from participants regarding their diagnoses, and after initial screening, records will be obtained from clinical records to confirm psychiatric diagnosis. In addition, information regarding disruptive behaviors necessitating intervention will be obtained for the 6 months prior to enrollment to establish a historical baseline of disruptive behaviors against which the efficacy of this study intervention will be compared. Clients with a history of at least one disruptive episode per week in at least 50% of the weeks in the 6-month period will be eligible for enrollment. At this early, feasibility stage, no stratification according to sex, gender, or ethnicity will be made.

Inclusion Criteria:

1. Age 18-65 years old
2. Diagnosis of Schizophrenia Spectrum, Bipolar, or Related Disorders
3. Presence of Anosognosia (SUMD: Minimum combined score of 4 on questions 1) and 2); Recent (at least <6 months) history of disruptive behaviors (at least 1 disruptive behavior per week in >50% of weeks in the 6-month period prior to enrollment)
4. Receive case management services through TDC
5. Ability to comply with study procedures
6. Willingness to participate in contingency management intervention

Exclusion Criteria:

Based on assessment by the client's case manager, the presence of:

1. Inability to provide informed consent
2. Unstable medical conditions that would interfere with participation
3. Cognitive impairment that would interfere with participation in the study
4. History of severe aggression or violent behavior posing a risk to study staff or other participants
5. Active suicidal ideation or a history of suicide attempts within the past 12 months

D. Research Design and Methods**Description of Study Intervention:**

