Subjects will be selected by Tulsa Day Center (TDC) staff based on inclusion criteria. Participants will meet weekly for 30 minutes with their case manager to discuss progress on life goals and determine if the bonus payment has been earned. The participant will receive \$10 for their time spent with the case manager each week. The goal is for the participant to maintain seven

days with no disruptive behaviors (or “trouble-free days”*) per week at each visit. This goal will be verified by the case manager and lead study manager prior to the participant’s visit each week using the sources of data information described below. When the goal is achieved for a certain week, the participant will receive payment. The payment starts at \$20 and each week the amount paid per goal/week will increase by \$1. Any week with disruptive behaviors will result in returning to the \$20 baseline amount.

*“Trouble free days” definition: Trouble-free days are days during which an individual with a severe mental disorder demonstrates no occurrence of problematic behaviors and maintains a stable mental state without causing harm or disruption to themselves or others.

Table 1: Possible Sources of Data for Baseline and Ongoing Trouble-Free Day Information:

- **Homeless Management Information System:** Shows current case manager, overnight shelter stays (recorded daily), VI SPIDAT scores.
- **Vulnerability Index Service Prioritization Decision Assistance Tool (VI SPIDAT):** records self-reported periods of homelessness, evictions, emergency room visits (physical reasons), hospitalizations (physical reasons), incarcerations, crisis care admissions, hospitalizations (mental health reasons), and substance use.
- **Oklahoma State Courts Network (OSCN):** Shows legal records including evictions, arrests, charges and disposition of cases.
- **City of Tulsa Jail Hub:** Shows City of Tulsa Municipal Court charges (trespassing, erecting an abode unlawfully, etc.)
- **Tulsa Police Department:** Source for arrest records
- **Tulsa Fire Department CARES program:** Tracks number of calls to 911
- **Tulsa City and County court records:** Data base for civil commitment municipal
- **Tulsa Center for Behavioral Health:** Inpatient stays
- **Grand Addiction Recovery Center and Grand Mental Health:** Participation in recovery programs
- **Landlords:** Mental Health Association Oklahoma, Hudson Villas, Tulsa Housing Authority
- **David L Moss Inmate Search:** Arrests and charges

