The study will be terminated for the following reasons: 1) participant misses 3 consecutive case manager visits, 2) at the determination of the participant's case manager when deemed necessary for safety reasons of the participant, staff, and milieu at TDC.

By implementing this detailed CM procedure, the study will be able to assess the feasibility and effectiveness of using positive reinforcement to promote behavior change among homeless individuals with psychotic disorders and anosognosia.

G. Statistical Methods

The statistical analysis for this study will be conducted using appropriate statistical software to ensure the validity and reliability of the results. The primary goal of the analysis is to evaluate the effectiveness of the CM program in preventing disruptive behaviors among homeless individuals with psychotic disorders and anosognosia.

Descriptive statistics will be calculated for all variables, including demographics, clinical characteristics, and outcome measures. These statistics will include measures of central tendency (mean, median) and dispersion (standard deviation, interquartile range) for continuous variables, as well as frequencies and proportions for categorical variables.

To compare the intervention and control historical period, we will employ Chi-square or Fisher's exact tests for the proportion of weeks free of disruptive behaviors.

The primary outcome measure will be the proportion of disruptive behavior-free weeks in the 6 months of the intervention compared with the previous 6 months. We will use linear or logistic regression models to analyze the relationship between these outcomes and the intervention,

adjusting for potential confounding factors such as age, gender, ethnicity, and baseline clinical characteristics, including psychiatric diagnosis.

For all statistical tests, a two-sided p-value of less than 0.05 will be considered statistically significant. To account for multiple comparisons, we will apply appropriate correction methods, such as the Bonferroni or Benjamini-Hochberg procedures.

In addition to the primary analysis, we will conduct exploratory subgroup analyses to assess the intervention's effectiveness among specific subpopulations, such as individuals with different levels of anosognosia severity, specific diagnoses within the Schizophrenia Spectrum or Bipolar and Related Disorders, or varying degrees of substance use.

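### The participant exit rule can be triggered by the behaviour being measured, and the protocol does not provide for collecting record-based events after exit

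*Protocol*

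**What the plan says.** Protocol section F, Reasons for Study Termination: "The study will be terminated for the following reasons: 1) participant misses 3 consecutive case manager visits". The second reason is a decision by the participant's case manager "when deemed necessary for safety reasons of the participant, staff, and milieu at TDC". What ends is called the study, not the visits or the payments.

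Section G gives the primary outcome as "the proportion of disruptive behavior-free weeks in the 6 months of the intervention compared with the previous 6 months".

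For the comparator, section C says that "information regarding disruptive behaviors necessitating intervention will be obtained for the 6 months prior to enrollment to establish a historical baseline". No exit rule applies to that period.

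During the intervention (section D), the weekly goal is verified before the participant's "visit each week using the sources of data information described below". Table 1 lists possible sources for baseline and ongoing use. The state courts network "Shows legal records including evictions, arrests, charges and disposition of cases", the fire department programme "Tracks number of calls to 911", and other entries cover jail, police and inpatient stays. None of these needs the participant to attend.

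Section C plans for 15 participants, with "10 completers estimating a very conservative attrition rate of 50" per cent. Section G adds sensitivity analyses for missing data, which may use multiple imputation.

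**The concern.** Both triggers can lie downstream of the outcome. Three weekly visits can be missed because the person is in jail after an arrest or has been admitted. A threat to staff or to the day centre is a disruptive event and also a ground for removal. Section B describes anosognosia, an entry criterion, as a predictor of both nonadherence and aggression, so exit and outcome share a stated cause. The payment scheme points the same way: a visit pays \$10 after a disruptive week and at least \$10 + \$20 = \$30 after a clean one.

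The protocol describes outcome checking only as a weekly step before a visit. Staff who treat the study as over for a participant could reasonably stop checking. The intervention period would then lose weeks for reasons linked to the outcome, while the retrospective baseline would lose none. In a before-after comparison of 15 people with no concurrent control, nothing else in the design would reveal that imbalance.

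This is not something a statistical analysis plan can settle. Whether records are obtained for someone who has left is a matter for the protocol and the consent form.

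**Working it through.** **Which reading of the rule.** The first trigger concerns one participant and the second that participant's case manager. The sensible reading is therefore that the rule ends one person's participation, not the whole trial. The rest assumes this.

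**Inputs.** 15 enrolled and 10 completers (section C); 50% attrition (section C); 76 weeks in 18 months (section J); 6 months taken as 26 weeks. Exit timing is not given and is assumed.

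**The plan's own attrition figures.** 15 enrolled and 10 completers means 5 exits, or 5/15 = 33%. Attrition of 50% of 15 means 7.5 exits. The two statements disagree, so both are carried forward.

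**Weeks at stake.** Intervention-side total = 15 × 26 = 390 person-weeks.

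Exits spread evenly over 76 weeks: exits in window = exits × 26/76, each losing 13 weeks on average.
- 5 exits: 5 × 26/76 = 1.71; × 13 = 22.2 weeks (5.7%).
- 7.5 exits: 7.5 × 26/76 = 2.57; × 13 = 33.4 weeks (8.6%).

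All exits at one week inside the window: weeks lost = exits × (26 − exit week).

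| Exit week | 5 exits | 7.5 exits |
|---|---|---|
| 20 | 30 (7.7%) | 45 (11.5%) |
| 13 | 65 (16.7%) | 97.5 (25.0%) |
| 6 | 100 (25.6%) | 150 (38.5%) |

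These are shares of weeks lost, not bias.

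**What lost weeks can do to the estimate (assumed rates).** Suppose 10 stayers have 60% disruption-free weeks, 5 leavers have 30%, and the leavers exit at week 8.
- All 26 weeks for everyone: (10 × 0.60 + 5 × 0.30)/15 = 0.50.
- Observed weeks only: (10 × 26 × 0.60 + 5 × 8 × 0.30)/(260 + 40) = 168/300 = 0.56.
- Completers only: 0.60.

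If leavers and stayers have the same rate, all three agree and there is no bias.

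A simulation of the three-missed-visits rule with no treatment effect gives smaller shifts. It assumed a mean disruption-free proportion of 0.40, Beta(4,6) variation between people, a 0.10 chance of missing the visit in a free week, 26 weeks, and 20,000 replicates of 15 people.

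| Chance of a miss in a disruptive week | Exit by week 26 | Observed weeks | Completers only |
|---|---|---|---|
| 0.10 | 2% | 0.400 | 0.400 |
| 0.40 | 33% | 0.410 | 0.434 |
| 0.50 | 49% | 0.418 | 0.462 |

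In the last row the overstatement is about 2 points on observed weeks and 6 points on completers, but it needs about half the cohort to exit within 26 weeks.

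**Weeks in custody or hospital.** Return to the 5 leavers at week 8 and suppose, as an extreme, that all 5 × 18 = 90 post-exit weeks are spent in jail or an inpatient unit. The result then depends on how those weeks are scored:
- Counted as disruption-free: (168 + 90)/390 = 0.66.
- Left out: 168/300 = 0.56.
- Counted as not disruption-free: 168/390 = 0.43.

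Collecting the records without a rule for such weeks could therefore replace one distortion with another.

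**The case against.** The strongest reply is that the protocol is silent, not prohibitive. Section F does not say that outcome collection stops. Table 1 describes its sources as ongoing, the primary outcome is not limited to attended weeks, and Clinical Monitoring in section F includes reviews of data completeness. The consent form is not in the text at hand and may already cover records after exit. A reader might infer that the protocol forbids post-exit collection. It does not, and that reading should be dropped. What stands is that the only described checking is tied to a visit, and section H limits collection to what the objectives require, so continuation cannot be presumed.

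A reader might also infer that the lost events could never be recovered. That goes too far: baseline events are collected retrospectively, and similar sources could be searched later if consent allows.

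A further reply concerns the question being asked. Weeks after exit carry no visits and no incentive, so including them moves from the effect while on the incentive to the effect of being offered it. Either is defensible in a small feasibility study. That is a reason to report both, and only the offered-it version needs post-exit data.

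Finally, the larger losses in the table require every exit over 76 weeks to fall in the first 26, and some exits will be consent withdrawals, which no fix should override. The protocol specifies no completers-only analysis. These points limit the size of the concern but do not remove it.

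**Conclusion.** The point holds in a limited form. On the participant-level reading, the rule ends follow-up on triggers that can result from the outcome, and nothing provides for collecting retrievable events afterwards. The intervention side can lose weeks selectively and the baseline cannot. With exits spread evenly, the loss is about 22 to 33 of 390 person-weeks (6% to 9%). Figures of 17% or more depend on early clustering that the protocol does not suggest.

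It is tempting to conclude that the results would be biased in favour of the intervention. The document does not support that. The bias is zero if exit is unrelated to behaviour. It is upward under the assumed rates above, and it could go the other way if the lost weeks would have been spent in custody and scored as clean. Size and direction are unknown.

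The planned missing-data sensitivity analyses mitigate this in part, but imputing events that could have been looked up is a poor substitute when exit may be informative. The change is worth making because it is cheap and each of the 15 participants carries much of the information.

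**What to change.** Amend section F and the matching text in sections D and G to state that:

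1. Three consecutive missed visits, or removal by the case manager, end the participant's visits and payments only.
2. Record-based disruptive events are collected for every enrolled participant to the end of the 6-month primary window, week by week or by one retrospective search, unless consent is withdrawn.
3. Weeks in jail or an inpatient unit are not counted as disruption-free by default. State whether they are left out or counted as not disruption-free, and apply the same rule to baseline weeks.
4. An analysis of pre-exit weeks only is reported alongside as a sensitivity analysis.

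Confirm that the consent form covers record access after exit, or amend it. It should also make clear how a participant withdraws that permission, since for some people ceasing to attend may be meant as withdrawal.

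The cost is a few sentences, possibly consent wording, and continued access to the kinds of record already checked weekly. There is a small privacy cost for people who have left or been removed. Elements that need contact, such as a stable mental state and self-report, will be less well ascertained after exit. This could make those weeks look cleaner than they were, so the report should say so.

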- **MyHealth Access Network:** Emergency room visits, hospital visits, diagnoses, medical care, prescribed medications, etc.
- **Julotta System:** will house information on hospital admissions, arrests, case management notes, medical history, list of medications prescribed, diagnosis, insurance info, ER visits in past 12 months, 911 calls in past 12 months, push notifications, referrals to other programs, program enrollments, past employment, strengths and abilities, financial assessment, past substance abuse. Julotta access will be dependent on implementation in the local community.
- **Other community-based services** as needed (e.g. Salvation Army, social security office, etc.)

Study Duration:

The involvement of each participant in this study will last 18 months. The study will last approximately 2 years.

Outcome:

Participants will decrease the frequency of disruptive behaviors, as defined above, in comparison with the 6-month period immediately prior to recruitment.

Sample Size:

This study exploring feasibility of the CM approach to resolve social dysfunctional behaviors will include up to 15 participants with the goal to obtain 10 completers.

Description of Sites/Facilities Enrolling Participants:

Tulsa Day Center in Tulsa, Oklahoma provides of full range of services and tools to assist clients in overcoming anticipated, situational and chronic homelessness. Their priority is to address client's basic needs: shelter, food, clothing and bathing. They offer rapid rehousing services, emergency shelter, medical assistance, and legal aid to help ensure all of those needs can be met. <https://tulsadaycenter.org/>

The Blue Team initiative at Tulsa Day Center was launched in September 2022, with the primary focus of working with a subset of the homeless population in Tulsa who have difficulty obtaining and maintaining safe housing due to anosognosia.

Baseline Assessment: The initial status of participants' target disruptive behaviors will be obtained from the 6 months prior to recruitment. This information will be used as a historical, preliminary comparator to the 6 months of CM intervention.

To evaluate the inclusion and exclusion criteria, the following procedures will be implemented:

- Diagnoses will be obtained from clinical records obtained by Tulsa Day Center.

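### Section G tests the two periods with chi-square or Fisher's exact tests on weeks, but the same 10–15 people supply about 26 weeks to each period, so the p-value does not hold its 5% level

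*Protocol*

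**What the plan says.** Section G names chi-square or Fisher's "exact tests for the proportion of weeks free of disruptive behaviors" for the comparison of intervention and historical periods. The primary outcome is that proportion over six months of intervention against the preceding six months, judged at two-sided p < 0.05. Section G adds: "We will use linear or logistic regression models to analyze the relationship between these outcomes and the intervention", adjusted for age, gender, ethnicity and baseline clinical characteristics.

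The comparator is not a separate group. Section C collects each participant's previous six months "to establish a historical baseline of disruptive behaviors against which the efficacy of this study intervention will be compared". The Baseline Assessment paragraph of Section D says of the same data: "This information will be used as a historical, preliminary comparator to the 6 months of CM intervention". The Sample Size paragraph of Section D plans "up to 15 participants with the goal to obtain 10 completers".

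Section G names no paired test, participant-level summary, mixed model, GEE or cluster-robust variance. Its sensitivity analyses (multiple imputation, propensity score matching) do not address dependence between weeks.

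**The concern.** Chi-square and Fisher tests on counts of weeks need independent weeks in two unrelated groups. Here the weeks are clustered within a handful of people, and the same people appear in both periods. The participant is the independent unit, not the week.

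The two faults act in opposite directions. Ignoring the pairing makes the test conservative when people differ only by a stable level. Ignoring the clustering makes it too liberal when people change by differing amounts or when disruptive weeks come in runs. The reader of the p-value cannot tell which applies.

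Pooling weeks may bring a second problem. Section C foresees "10 completers estimating a very conservative attrition rate of 50"%, and Section F lists "participant misses 3 consecutive case manager visits" as a reason for termination, read here as ending that person's participation. If everyone enrolled is analysed, early leavers give a full baseline but fewer intervention weeks. The mix of people then differs between periods.

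At stake is the trial's main claim, because Section G makes effectiveness the primary goal of the analysis and sets a significance threshold for it.

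**Working it through.** The protocol states no power, variance or intraclass correlation for this test, so there is no figure to reproduce. The check is whether the test keeps its 5% level.

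**Inputs.** From the protocol: 10 to 15 people, two periods of six months, two-sided 0.05. Derived: about 26 weeks per period. Assumed: all variances and correlations.

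**Weeks counted as independent.** 15 × 26 = 390 per period, 780 in all; 10 × 26 = 260 per period, 520 in all.

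**Analytic check.** Let ICC be the correlation between weeks of one person in one period, and s the share of person variance common to both periods. The true variance of the period difference, relative to what chi-square assumes, is

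F = 1 + 25·ICC − 26·ICC·s, with true level = 2·[1 − Φ(1.96/√F)].

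Example, ICC 0.10: s = 0 gives F = 1 + 2.5 = 3.5 and a level of 0.295; s = 0.5 gives F = 3.5 − 1.3 = 2.2 and 0.186; s = 1 gives F = 3.5 − 2.6 = 0.9 and 0.039.

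| ICC (assumed) | s = 0 | s = 0.5 | s = 1 |
|---|---|---|---|
| 0.02 | 0.110 | 0.078 | 0.048 |
| 0.05 | 0.191 | 0.121 | 0.044 |
| 0.10 | 0.295 | 0.186 | 0.039 |
| 0.20 | 0.424 | 0.288 | 0.028 |
| 0.30 | 0.501 | 0.361 | 0.019 |

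**Simulation, no true effect, no entry rule.** 10 or 15 people, 26 weeks per period, person effect with SD 1 on the logit scale. The test is the uncorrected chi-square on pooled weeks.

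- People differ only in level: rejects about 3%.
- Each person's logit also varies independently in each period, SD 0.25 / 0.5 / 0.75 / 1.0 (true change SD about 7 / 14 / 21 / 26 percentage points): 6–7% / 15–16% / 25–27% / about 35%. Fisher's test is similar, 33% at SD 1.0.
- Week-to-week correlation 0.2 / 0.4 / 0.6, with person SD 1 or with one common probability for all: 7–11% / 15–20% / 25–31%.
- Pooled logistic regression with four person-fixed covariates: 17–18% at SD 0.5 and 36% at SD 1.0. These covariates were random, so this shows only that adding covariates does not cure the dependence.
- Paired t-test on participant changes, across a grid of person-variation and carry-over settings: 4.3–5.6%.

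**Early leaving.** 15 enrolled, 5 leave after 4–12 weeks, everyone's weeks pooled, level differences only. Chi-square rejects 7% if leaving is unrelated to disruption. If the more disruptive leave more often, it rejects 22–24% with a spurious gain of 4.5 percentage points. Five of 15 is the loss that leaves the planned 10 completers. The stated 50% would leave 15 × 0.5 = 7.5.

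**With the entry rule.** Section C requires "at least one disruptive episode per week in at least 50% of the weeks in the 6-month period". People were kept only if at least 13 of 26 baseline weeks were disruptive (n = 15, person SD 1, assumed source-population median of 27–73% disruption-free weeks):

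| Per-period SD | Chi-square rejects | Paired t rejects |
|---|---|---|
| 0 | 5–30% | 6–30% |
| 0.5 | 22–78% | 8–53% |

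With level differences only, pairing gains nothing here. With person-by-period variation it gains much, but not a 5% test. What is left comes from selecting people on a bad baseline.

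**The case against.** The best case for the plan has five parts.

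- **The test may be conservative.** This is true if people differ only in level and weeks are otherwise independent. It would require everyone to respond alike and disruption not to come in runs. The entry rule also narrows the baseline spread, which makes that case less likely. The point limits what can be said about direction but does not rescue the p-value.
- **The remedy is not valid under the real entry rule either.** This stands. The paired test corrects the unit and the pairing; regression to the mean needs a separate answer.
- **The dropout bias depends on the analysis set.** This stands. If only completers are analysed, each gives two full periods and the person-mix shift does not arise. Section G also plans sensitivity analyses for missing data. The dropout figures are conditional on pooling everyone enrolled.
- **A participant term could be left to the SAP.** This has some force for the regression sentence, and linear regression could mean person-level proportions. It has none for chi-square and Fisher on weeks, which are named tests that do not fit the design.
- **This is a feasibility study with a preliminary comparator.** Sections C and D say so, but Section G makes effectiveness the main analytical goal at p < 0.05.

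**Conclusion.** The concern holds. The protocol fixes an unsuitable test for its primary comparison, and nothing else in Section G repairs it. The nominal 5% level is kept only if everyone has the same weekly probability and weeks are independent, which is implausible in this population.

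Without the entry rule, the simulated level of the chi-square test runs from about 2–3% (stable differences only) to about 35% (large person-by-period variation). The analytic extreme is 50% at ICC 0.30 with nothing shared between periods. All of these rest on assumed variances. That the level is uncontrolled, in a direction nobody can state in advance, follows from the design alone. This must be fixed before analysis.

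**What to change.** In Section G, replace the chi-square/Fisher sentence with, for example: *For each participant we will calculate the change in the proportion of disruption-free weeks, intervention window minus baseline window. The mean change will be tested with a two-sided paired t-test, with the participant as the unit, and reported with its 95% confidence interval.* An exact Wilcoxon signed-rank test is an alternative, but one test must be chosen in advance. The t-test matches the interval for the mean change.

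If a regression is kept, use a logistic mixed model with a participant random intercept and random period effect, or a GEE clustered on participant with small-sample correction. Neither was simulated here at 10–15 people. In a within-participant comparison, person-fixed covariates are largely redundant, and with so few people they risk overfitting.

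State which participants are analysed and how early leavers' weeks are used. State also that the change corrects the unit of analysis and the pairing only, and removes neither regression to the mean from the entry rule nor every dropout bias.

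The cost is a wording change and no new data. The confidence interval will usually be wider than one from pooled weeks, or slightly narrower if people differ only in level.

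### Section G gives the one primary outcome two unranked analyses, and neither, as named, uses the pairing of the same 10 to 15 people across both periods

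*Protocol*

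**What the plan says.** All of this is in Protocol section G, Statistical Methods.

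- The primary outcome is the "proportion of disruptive behavior-free weeks in the 6 months of the intervention compared with the previous 6 months".
- For comparing the two periods: "we will employ Chi-square or Fisher's exact tests for the proportion of weeks free of disruptive behaviors".
- Directly after the primary outcome is defined: "We will use linear or logistic regression models to analyze the relationship between these outcomes and the intervention". The models are to be run "adjusting for potential confounding factors such as age, gender, ethnicity, and baseline clinical characteristics, including psychiatric diagnosis".
- The decision rule: "For all statistical tests, a two-sided p-value of less than 0.05 will be considered statistically significant".

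The paragraph on subgroups then speaks of a primary analysis as if it had been identified. No sentence does so, and no rule covers the case where the two routes give different answers.

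Sample size is in sections C and D: up to 15 participants, with 10 completers as the goal. Each participant is compared with their own preceding 6 months.

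**The concern.** Section G makes effectiveness the main goal of the analysis and attaches a significance threshold to it, so a reader must be able to tell which p-value decides. Here two analyses of the same contrast are both promised and neither is ranked.

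The second difficulty is that the design is before-and-after in the same people. Chi-square and Fisher tests on week counts treat every week as an independent unit. Linear or logistic regression, as named, adjusts for characteristics of the person but has no term that links a person's two periods. With 10 to 15 people, ignoring the link can make a test too liberal or far too conservative, depending on which listed test is used. At stake is whether the program is reported as effective or as not shown to be effective.

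**Working it through.** **What there is to reproduce.** The only stated figure is the 0.05 level. The protocol gives no effect size, standard deviation or power, so what follows rests on assumptions.

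**Inputs.** From the protocol: 10 completers, up to 15 enrolled, 6 months per period, and eligibility requiring disruption in more than half of baseline weeks (so a free share below 50%). Assumed: w = 26 weeks per period, baseline free share p = 0.35, between-person SD 0.5 on the logit scale, and SD τ of the person-specific change equal to 0, 0.4 or 0.8 logit.

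**Step 1: pooled chi-square with no average change.** Write v = p(1−p) = 0.35 × 0.65 = 0.2275.

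- Per-person variance of the difference in proportions, approximately: 2v/w + v²τ².
- Variance that the pooled test assumes: 2v/w = 2 × 0.2275/26 = 0.0175.
- Extra term: v²τ² = 0.05176 × τ², which is 0.0083 at τ = 0.4 and 0.0331 at τ = 0.8.
- Ratio of true to assumed variance: 0.0258/0.0175 = 1.47 and 0.0506/0.0175 = 2.89.
- Effective critical value: 1.96/√1.47 = 1.61 and 1.96/√2.89 = 1.15.
- False-positive rate: about 11% and 25%, against 5% at τ = 0.

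The number of people cancels, so this does not improve from 10 to 15. Simulation under the same inputs gives 4-5%, about 10% and 22-23%.

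**Step 2: unpaired linear regression of person-period proportions, no average change.** This model leaves the between-person spread in its error.

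- Variance it assumes: 2(v/w + v² × 0.5²) + v²τ².
- At τ = 0: 2 × (0.00875 + 0.01294) = 0.0434, against a true 0.0175 (ratio 0.40).
- At τ = 0.8: 0.0434 + 0.0331 = 0.0765, against a true 0.0506 (ratio 0.66).
- With 10 people (18 degrees of freedom, critical value 2.101), the effective critical values are 2.101/√0.403 = 3.31 and 2.101/√0.662 = 2.58.
- Rejection rates on the t scale: about 0.4% and 1.9%. Simulation gives 0.4-2%.

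**Step 3: participant-level paired test.** Its error term is the observed spread of the within-person differences, so it includes v²τ². Simulated false-positive rate: 4-6% throughout.

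**Step 4: disagreement when there is a true gain.** For gains of roughly 9 to 15 percentage points and 10 or 15 people, Fisher on pooled weeks and the unpaired linear regression fall on opposite sides of 0.05 in about 17-46% of simulated trials. Replacing the linear model by week-level logistic regression lowers disagreement to at most 3.7% against Fisher and 0.2% against chi-square.

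**Step 5: a borderline example within the first route.** With 260 weeks per period (10 × 26), take 104 free weeks before and 127 during. The difference is 23/260 = 0.0885 and the pooled share 231/520 = 0.444. The standard error is √(0.444 × 0.556 × 2/260) = 0.0436, so z = 2.03. Chi-square p = 0.042; Fisher p = 0.052.

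**The case against.** The strongest reply has four parts.

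**Detail for the SAP.** Chi-square or Fisher, linear or logistic, and the covariate list are often settled in an SAP, which may exist. An unadjusted comparison followed by an adjusted model is also a conventional sequence. This stands for those choices taken singly. It does not cover a protocol that itself sets out both routes for one outcome, applies one threshold to both, and refers to a primary analysis that it does not identify.

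**False positives from choosing among tests.** A reader might infer that picking the most favorable listed test is what inflates the error rate. The calculations do not support that. In null trials, linear regression was practically never significant when chi-square was not, and the listed tests together rejected about as often as chi-square alone. The excess comes from pooling repeated weeks.

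**The correction sentence.** A reader might also infer that the primary threshold is left open because "we will apply appropriate correction methods, such as the Bonferroni or Benjamini-Hochberg procedures". That sentence concerns multiple comparisons in general and gives its methods as examples. Nothing ties it to the primary hypothesis, and the exploratory subgroups that follow are a natural family for it.

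**The disagreement depends on the model.** The protocol does not fix the unit of the linear regression. The 17-46% belongs to an assumed unpaired model of person-period proportions and is not a general property of the listed tests. This stands, and the figure should be quoted only with that condition.

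The study is also small and described as an early feasibility stage, which limits the consequence. Section G nevertheless sets an effectiveness goal with a significance rule.

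**Conclusion.** The point holds in this form: one primary outcome, two unranked analyses at the same 0.05 level, no identified primary analysis, and no listed test that, as named, uses the pairing. It should be corrected, but it is not a fatal flaw.

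The pooled test is close to nominal if everyone changes alike, and at 10-23% false positives if the change varies between people with SD 0.4-0.8 logit. The unpaired linear model errs the other way, at 0.4-2%. All these sizes rest on the assumed 26 weeks, free share of 0.35 and person SD of 0.5 logit; none of these is a protocol figure. The simulated weeks are also independent within a person and period, which is itself an assumption.

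**What to change.** In section G, name one primary analysis: a participant-level paired comparison of the proportion of disruptive behavior-free weeks. Take one difference per participant and test it with a paired t test or an exact signed-rank or permutation test, the choice made in advance. Use two-sided 0.05 and report the mean or median difference with its 95% confidence interval. State that the chi-square or Fisher and regression results are supportive and cannot replace it.

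The change is a rewording of two or three sentences and needs no new data. It has two costs. Apparent power is lower than with pooled weeks: in a simulation with 10 people, baseline log-odds −0.4, person SD 0.8 and a log-odds gain of 0.4, the paired t test rejected in 47% of trials against 51% for chi-square when everyone changed alike, and in 22% against 51% when the change had SD 0.8. In the second setting chi-square also rejected in 20% of trials with no average effect, so its higher figure is not a true gain in power. The other cost is that a favorable supportive model can no longer be presented as the main result.
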